4.1 Primary Objective

The primary objective of this study is to assess whether an intravenous infusion of hMSCs in patients with ARDS will lead to a reduction in the severity of acute respiratory failure from ARDS as measured by the oxygenation index.

4.2 Secondary Objectives

The secondary objectives of this study are to assess the potential efficacy of intravenous infusion of hMSCs in patients with ARDS including (1) an improvement in several physiologic and functional endpoints of respiratory failure, (2) a reduction in the incidence of secondary infections, (3) a reduction in systemic organ failure and in-hospital mortality, (4) improved neurocognitive function at hospital discharge, (5) incidence of thromboembolic events, as well as (6) to acquire mechanistic data regarding the activity of hMSCs in ARDS patients from biologic samples of plasma, urine and mBAL. In addition, safety will be monitored as defined by the incidence of pre-specified infusion associated events and of unexpected severe adverse events in ARDS patients treated with hMSCs. Because the vast majority of patients enrolled in this trial will have had ARDS secondary to COVID-19, all of the objectives will be analyzed according to whether the patient developed ARDS from COVID-19 or another etiology.

5 Study Design

This clinical study design is a randomized, double-blinded, placebo-controlled Phase 2b clinical trial using a 10×10^6 cell/kg dose of hMSCs. Subjects will be randomized in a 1:1 randomization scheme to receive hMSCs or cell reconstitution media (1:1 mix of 5% human serum albumin and 10% Dextran 40) as the placebo; the study will enroll 120 patients who achieve a stable clinical baseline and receive study product (either hMSCs or the placebo) as described in **Section 9.4**.

The DSMB will review adverse outcomes and protocol compliance. A pre-specified interim review will occur after 60 subjects have been enrolled and received study product; enrollment will continue during DSMB review. All pre-specified clinically important events and unexpected serious adverse events including death through day 28 from study product administration will be reported to the DSMB on an ongoing basis; the study will be stopped for a safety evaluation by the DSMB if they have any concerns or if three subjects have pre-specified clinically important events or unexpected serious adverse events EXCEPT death since death will be common in this critically ill population due the nature of the underlying illness (e.g., ARDS).

6 Endpoints

Analyses of the primary and secondary endpoints will be conducted primarily as an intention-to-treat analysis plan and also an as-treated analysis as described in detail in **Section 11.3**. A Statistical Analysis Plan has been written according to this protocol. There is the potential for subjects to be consented for study participation but to not receive treatment because of clinical instability due to the severity of their underlying medical conditions or due to clinical improvement in ARDS.

6.1 Primary Study Endpoint: Phase 2b

The primary study endpoint will assess whether an intravenous infusion of hMSCs in patients with ARDS will lead to a reduction in the severity of ARDS as measured by a decrease in the oxygenation index (OI) compared to baseline OI (prior to administration of the study product) over the first 36 hours after the initiation of study product infusion (with measurements of OI at 6, 12, 18, 24, 30 and 36 hours). (125, 126)

6.2 Secondary Endpoints: Phase 2b

6.2.1 Efficacy Secondary Endpoints

We will test six categories of efficacy endpoints in the Phase 2b trial: respiratory physiology, secondary infection, systemic illness, neurologic, thromboembolic events, and biomarker profiles related to potential mechanism of hMSC activity in ARDS.

1. Respiratory Physiology: Respiratory efficacy endpoints will include:

- Reduction in the 4-point acute lung injury (LIS) score after enrollment in the trial at days 1, 2, 3 and 7, or on the last day of positive pressure ventilation prior to day 7. The LIS is a composite scoring system including the $\text{PaO}_2/\text{FiO}_2$, the level of positive end-expiratory pressure, static respiratory compliance, and the quadrants of frontal chest radiograph with opacification.
- Reduction in the pulmonary dead space on days 1, 2, 3 and 7.
- Reduction in chest radiograph assessment of the extent of pulmonary edema (RALE score) at days 1, 2, 3, and 7.
- OI will be collected (as planned) also on days 2, 3, and 7 if still being ventilated with positive pressure as a secondary endpoint.
- Reduction in ventilatory ratio with measurements at 6, 12, 18, 24, 30, 36 hours, and days 2, 3 and 7.
- Incidence of barotrauma on days 1, 2, 3, and 7.
- Achieving pressure support ventilation with 5 cmH_2O and positive end-expiratory pressure equals to 5 cmH_2O for 2 hours
- Ventilator free-days over 7, 14 and 28 days; duration of assisted ventilation over 28 days in the survivors. Ventilator Free Days (VFDs) to day 28 are defined as the number of days from the time of initiating unassisted breathing to day 28 after study product

administration, assuming survival for at least two consecutive calendar days after initiating unassisted breathing and continued unassisted breathing to day 28. If a patient returns to assisted breathing and subsequently achieves unassisted breathing to day 28, VFDs will be counted from the end of the last period of assisted breathing to day 28. A period of assisted breathing lasting less than 24 hours and for the purpose of a surgical procedure will not count against the calculation of VFDs. If a patient was receiving assisted breathing at day 27 or dies prior to day 28, VFDs will be zero. Patients transferred to another hospital or other health care facility will be followed to day 28 to assess this endpoint.

2. Secondary Infection: Infection efficacy endpoints will include:

- Superficial incisional/wound infections during the 14 days after enrollment.
- Deep incisional wound infections during the 14 days after enrollment.
- Organ (such as lung, liver) or space (such as peritoneum or pleural) infections during the 14 days after enrollment.
- Ventilator associated pneumonia (VAP) during the 14 days after enrollment.

3. Systemic Illness: Systemic illness efficacy endpoints will include:

- Mean SOFA score (127) at days 3, and 7.
- In hospital mortality at 14 days, 28 days, and 60 days.
- Additional prognostic value of neutrophil:lymphocyte ratio.
- Ordinal Scale for Clinical Improvement (OSCI) at days 7, 14 and 28.

To assess organ failure, we will measure serum creatinine (renal function), bilirubin (hepatic function), and platelet count (hematology) at days 0, 3, and 7.

4. Neurologic: Neurocognitive efficacy endpoints will include:

- Neurocognitive function at hospital discharge by the Glasgow Outcome Score (6 points)

5. Thromboembolic: Thromboembolic safety endpoints will include:

- Incidence of thromboembolic events: Measured by ultrasound of the deep venous system or CT-angiography of the chest when clinically indicated.
- Additional prognostic value of fibrinogen at baseline.

6. Biologic: Biomarker analysis will include: Changes in levels of plasma, urine, and genetic biomarkers at baseline compared to 6, 24, 48, and 72 hours, including:

- Endothelial injury (angiopoietin-2 [Ang-2])
- Lung epithelial injury (Receptor for Advanced Glycation Endproducts [RAGE])
- Pro-inflammatory markers (interleukin-6, interleukin-8, soluble tumor necrosis factor-1 [sTNF-1], intercellular adhesion molecule-1 [ICAM-1], interferon gamma-induced protein-10 [IP-10], interleukin-10 [IL-10], vascular endothelial growth factor [VEGF], matrix metalloproteinase-8 [MMP-8], thrombomodulin, surfactant protein-D [SP-D], triggering receptor expressed on myeloid cells-1 [TREM-1], interleukin-18 [IL-18], plasminogen activator inhibitor-1 [PAI-1])

- Protein C (marker of impaired coagulation)
- Pro-resolving lipids (lipoxin A4, resolvin D₁)
- Biomarkers that reflect the paracrine activity of the administered hMSCs (angiopoietin-1 [Ang-1], keratinocyte growth factor [KGF])
- We will use the levels of the baseline plasma biomarkers (IL-8, Protein C, and serum bicarbonate ± vasopressor use at randomization) to classify patients as hyper- or hyper-inflammatory subphenotypes as we have described and test for higher mortality in the hyper-inflammatory group. Also, we will test for an interaction between MSC therapy and the subphenotypes for the outcomes of oxygenation index over 36 hours and 28 day mortality.
- Lung protein permeability as measured by total protein in mini-bronchoalveolar lavage [mBAL] protein at day 2; the same biomarkers will also be measured in plasma to compare MSC versus placebo treated patients.
- Measurements of urine microalbumin and urine creatinine
- Changes in levels of plasma SARS-CoV-2 viral antigen and antibody at multiple timepoints.
- Gene expression at baseline and on days 2 and 3.

6.2.2 Safety Secondary Endpoints

Because the infusion of hMSCs could theoretically, as described above, cause transient occlusion of the pulmonary microcirculation which could be associated with a fall in systemic blood pressure, rising vasopressor dose, a rise in heart rate, an increase in arterial carbon dioxide concentration, or a fall in oxygenation, patients will be monitored closely during the study infusion for changes in these parameters. These events will be considered pre-specified infusion associated events if they occur within 6 hours of the initiation of study product infusion.

Pre-specified infusion associated events will be defined as:

(a) Within 6 hours of the initiation of study product infusion:

1. An increase in vasopressor dose greater than or equal to the following:
 - Norepinephrine: 10 mcg/min
 - Phenylephrine: 100 mcg/min
 - Dopamine: 10 mcg/kg/min
 - Epinephrine: 0.1 mcg/kg/min
 - Addition of a third vasopressor
2. New ventricular tachycardia, ventricular fibrillation or asystole
3. New cardiac arrhythmia requiring cardioversion
4. Hypoxemia requiring an increase in FiO₂ of 0.2 or more and an increase in PEEP of 5 cmH₂O or more to maintain SpO₂ in the target range of 88-95% that is not related to respiratory care/suctioning or ventilator dyssynchrony and persists for more than 30 minutes
5. Clinical scenario consistent with transfusion incompatibility or transfusion-related infection (e.g. urticaria, rash, new bronchospasm)

(b) Within 24 hours of the study product infusion:

1. Any cardiac arrest or death

We will also systematically collect and review the incidence and nature of serious adverse events that are different from what is expected in the clinical course of a critically ill patient with ARDS for the duration of the clinical trial (through day 28 from study product administration).

Expected events for ARDS are untoward clinical occurrences that are perceived by the investigator to occur with reasonable frequency in the day to day care of patients with ARDS treated in an intensive care unit with mechanical ventilation. Examples of adverse events that are expected in the course of ARDS include transient hypoxemia, agitation, delirium, nosocomial infections, skin breakdown, and gastrointestinal bleeding. Such events, which are often the focus of prevention efforts as part of usual ICU care, will not be considered reportable adverse events unless the event is considered by the investigator to be associated with the study drug or procedures, or unexpectedly severe or frequent for an individual patient with ARDS. Examples of unexpectedly frequent adverse events would be repeated episodes of unexplained hypoxemia. This would be in contrast to an isolated episode of transient hypoxemia (e.g. Sp₀₂ ~85%), related to positioning or suctioning. This latter event would not be considered unexpected by nature, severity or frequency.

For this Phase 2b study, the secondary safety endpoint will be the incidence of pre-specified infusion associated events occurring within 6 hours of study product administration and any cardiac arrest or death occurring within 24 hours of study product administration, as well as any unexpected severe adverse events in ARDS patients (not including death because it is expected in ARDS) treated with hMSCs compared to patients treated with placebo through day 28 from study product administration.

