9.4 Investigational Product Administration

The investigational product will be administered intravenously according to the following dose schedule. The investigational product (h MSCs or placebo) will be administered intravenously over approximately 60-80 minutes.

We will enroll 120 patients in a 1:1 blinded, randomized, placebo-controlled design with the dose of 10×10^6 viable cells/kg (60 patients treated with hMSCs and 60 controls), with viability determined at the time of cell preparation at UMMC. Safety analyses will be conducted by the independent DSMB, and the sponsor and investigators will remain blinded. The safety reviews will be conducted after treatment of 60 patients, and the trial will continue during these analyses.

Critically ill patients often experience minute-to-minute changes in vital signs. Investigators will begin the infusion of hMSCs after a stable baseline for 2 hours has been observed.

A. Stable baseline will be defined as:

- a. Transcutaneous oxygen saturation in the target range of 88-95% without any increase in ventilator settings **AND**
- b. Stable vasopressor use if the patient requires vasopressors for blood pressure support. The dose of vasopressor may be increased a small amount during this 2-hour period, predefined as: no more than a 5 mcg/min increase in norepinephrine dose; no more than a 50 mcg/min increase in phenylephrine dose; no more than a 5 mcg/kg/min increase in dopamine dose; and no more than a 0.05 mcg/kg/min increase in epinephrine dose.

B. The following patients will be considered clinically unstable and will **NOT** receive the study product:

- a. Patients requiring an increase in FiO₂ of 0.2 or more and an increase in PEEP of 5 or more to maintain SpO₂ in the target range of 88-95%
OR
- b. Patients who require 3 vasopressors for blood pressure support and/or the use of > 0.1 mcg/kg/min of epinephrine for blood pressure support,

OR

[figure not shown]
- c. Patients who do not meet stability criteria in the supine or prone position,
OR
- d. Patients who have evidence of ongoing bleeding by the requirement of more than 3 units of packed red blood cells during the prior 24 hours prior to randomization.

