C. Patients who are clinically unstable will be monitored closely; if they achieve a stable baseline within 14 days of meeting the entry criteria for the study and, at the time of the stable baseline, still meet criteria for ARDS ($\text{PaO}_2/\text{FiO}_2 < 250$ with bilateral infiltrates and no evidence of left atrial hypertension) with a PEEP of ≥ 5 , they can receive the study product if the study product can be initiated within 14 days of initial ICU admission.

D. To confirm study product eligibility, an arterial blood gas will be obtained within 90 minutes prior to beginning the baseline stability period. Patients will not receive the study product infusion if the $\text{PaO}_2/\text{FiO}_2$ ratio is equal or greater than 250 mmHg on this pre-infusion arterial blood gas. Subjects who do not initiate the infusion of study product (e.g., not obtain 2 hours of stable baseline, increased $\text{PaO}_2/\text{FiO}_2 \geq 250$, study withdrawn, et al.) will be excluded from patient accruals and from the data analyses. They will not be included in an intention to treat analysis. Arterial blood gases will also be obtained at the end of the study product infusion (~1 hour) and at 6, 12, 18, 24, 30 and 36 hours (+/- 1 hour for all timepoints) after the initiation of study product infusion.

E. To summarize the timelines for eligibility for the trial, see these key criteria and the timeline:

- Eligibility for the trial - ARDS develops less than 72 hours since first meeting ARDS criteria per the Berlin definition of ARDS.
- Eligibility for the trial - Must begin to administer study product within 14 days of initial ICU admission
- Eligibility - The $\text{PaO}_2/\text{FiO}_2$ remains less than 250 mmHg after consent obtained and within 90 minutes prior to beginning the baseline stability period.

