12.1 Definitions

Investigators will determine daily if any clinical adverse experiences occur during the period from enrollment through study day 28 after investigational product administration. The investigator will evaluate any changes in laboratory values or physical signs, and will determine if the change is clinically important and different from what is expected in the course of treatment of patients with ARDS.

For this trial, a reportable adverse event is defined as:

Any clinically important untoward medical occurrence in a patient receiving study product which is different from what is expected in the clinical course of a patient with ARDS, or:

1. Any clinically important, untoward medical occurrence that is thought to be associated with the study product, regardless of the “expectedness” of the event for a patient with ALI, or
2. The following pre-specified infusion associated events occurring within 6 hours from the start of study product will always be reported as adverse events:

- If on a vasopressor, an increase in vasopressor dose greater than or equal to the following:
 - Norepinephrine: 10 mcg/min
 - Phenylephrine: 100 mcg/min
 - Dopamine: 10 mcg/kg/min
 - Epinephrine: 0.1 mcg/kg/min
 - Addition of a third vasopressor
- New cardiac arrhythmia requiring cardioversion OR ventricular tachycardia, ventricular fibrillation or asystole
- Hypoxemia requiring an increase in FiO₂ of 0.2 or more and an increase in PEEP of 5 cmH₂O or more to maintain SpO₂ in the target range of 88-95% that is not related to respiratory care/suctioning or ventilator dyssynchrony and persists for more than 30 minutes
- Clinical scenario consistent with transfusion incompatibility or transfusion-related infection (e.g. urticaria, new bronchospasm)

3. Any cardiac arrest or death that occurs within 24 hours from the start of study product will be reported as a pre-specified, infusion-associated significant event. Any cardiac arrest or death that occurs during the study period will be a reportable event that will be reviewed in detail.

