12. Adjust F_1O_2 or PEEP downward within 30 minutes if there are consistent measurements above the oxygenation target range.
13. There are no requirements for maintaining a specific PEEP to F_1O_2 ratio. The lower PEEP/higher F_1O_2 table represents a consensus approach developed by ARDS Network investigators in 1995. The higher PEEP/lower F_1O_2 table (ALVEOLI) yielded equivalent results in a randomized trial (Brower et al., 2004) and would be acceptable and perhaps preferable in patients who appear to respond with a substantial increase in arterial oxygenation in the transition from lower to higher PEEP.

Lower PEEP/Higher F_1O_2 Treatment Group

F_1O_2	.30	.40	.40	.50	.50	.60	.70	.70	.70	.80	.90	.90	.90	1.0
PEEP	5	5	8	8	10	10	10	12	14	14	14	16	18	18-24

Higher PEEP/Lower F_1O_2 Study Group

F_1O_2	.30	.30	.30	.30	.30	.40	.40	.50	.50	.50 – .80	.80	.90	1.0	1.0
PEEP	5	8	10	12	14	14	16	16	18	20	22	22	22	24

Note: Levels of PEEP in these F_1O_2 / PEEP tables represent levels set on the ventilator, not levels of total-PEEP, auto-PEEP, or intrinsic-PEEP.

14. No specific rules for respiratory rate. It is recommended that the respiratory rate be increased in increments to a maximum set rate of 35 if $pH < 7.30$.
15. No specific rules about I:E. It is recommended that duration of Inspiration be \leq duration of Expiration.
16. Bicarbonate is allowed (neither encouraged nor discouraged) if $pH < 7.30$.
17. Changes in more than one ventilator setting driven by measurements of PaO_2 , pH , and P_{plat} may be performed simultaneously, if necessary.

References:

The Acute Respiratory Distress Syndrome Network. Ventilation with lower tidal volumes as compared with traditional tidal volumes for acute lung injury and the acute respiratory distress syndrome. The Acute Respiratory Distress Syndrome Network. 2000; 342:1301-1308.

2. Weaning

Commencement of Weaning (applicable to patients ventilated invasively or non-invasively):

Patients will be assessed for the following weaning readiness criteria each day between 0600 and 1000. If a patient procedure, test, or other extenuating circumstance prevents assessment for these criteria between 0600 and 1000, then the assessment and initiation of subsequent weaning procedures may be delayed for up to six hours.

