Appendix G. Mini-Bronchoalveolar Lavage Procedure

The mini-BAL procedure involves blind specimen sampling from distal airspaces of patients with endotracheal or tracheal intubation. Specimens are obtained with the Combicath™ (Plastimed) catheter that is commonly used for the diagnosis of ventilator-associated pneumonia. The catheter is introduced from its protective sheath into the endotracheal or tracheal tube through a standard bronchoscopy adapter, and then gently advanced into the lungs until it becomes wedged in a distal airway. The catheter then is withdrawn approximately 3 cm to allow room for the inner catheter to be advanced into the distal airway. This is accomplished by removing the white protective spacer and gently advancing the inner catheter to its full length and securing it to the outside catheter by slightly twisting it into the outside catheter. Then, two 30-mL syringes containing 20 mL normal saline and a 5mL air bolus are injected rapidly into the lungs. Once the air bolus clears the second syringe, gentle aspiration is applied to the syringe for approximately 10 seconds to retrieve as much of the instilled fluid as possible (usually 5-10 ml). When completed, the catheter is removed from the endotracheal tube. The recovered aspirated samples are then emptied into a standard screw-top specimen container used for BAL samples. If the clinical condition warrants it, 1 ml can be deposited into a sterile container to be sent to the microbiology laboratory for culture.

Note: The mini- BAL procedure can be done with either one or two clinicians but it is easier to do (and typically more effective) when two clinicians are involved: one to advance, wedge, and manipulate the Combicath and the other to instill and aspirate the lavage. The patient should be pre-oxygenated on an FiO₂ of 1.0 for 10 minutes prior to the procedure and routine endotracheal suctioning should be done first to remove sputum from the airways.

After the mini- BAL, routine suction should be repeated to remove any excess BAL fluid that may be present in the airways. Assess patient's oxygenation and ventilatory status and return patient to their baseline FiO₂ when clinically indicated, usually within 5-10 minutes. The ventilator circuit should be returned to its original configuration by replacing the bronchoscopy swivel adapter with a clean adapter that was originally present in the circuit.

The mini-BAL should NOT be performed under the following circumstances:

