1. FiO₂ greater than 0.70 AND PEEP greater than 14 cm H₂O
2. Hemodynamic instability (despite fluid resuscitation/pressor support)
3. Open external ventricular device or intracranial pressure greater than 15mmHg or unstable
4. Most recent INR greater than 2.0 or PTT > 40
5. Most recent Platelets less than 50x10³/mm³ (within 36 hours of BAL)

Since this is a study procedure, any associated adverse event should be reported as a study related event. Transient hypoxemia is considered an expected event for ARDS, but prolonged or severe hypoxemia following mini-BAL should be reported as an adverse event.

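### The pre-specified hypoxemia item cannot be met by a patient infused at FiO2 above 0.80, so this named harm is under-counted in both arms

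*Protocol*

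**What the plan says.** Protocol 6.2.2 names a fall in oxygenation among the theoretical harms of transient occlusion of the pulmonary microcirculation. Its hypoxemia item requires an FiO2 increase "of 0.2 or more and an increase in PEEP of 5" cmH2O or more to keep SpO2 within 88-95%. The episode must also be one "that is not related to respiratory care/suctioning or ventilator dyssynchrony and persists for more than 30 minutes". Protocol 12.1 uses the same joint condition, "of 0.2 or more and an increase in PEEP of 5 cmH₂O or more", and puts the item among the events that are always reported. SAP 7.2.2 repeats it. None of the three places offers another way to qualify.

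The item is used in three ways:
- It is part of the secondary safety endpoint (Protocol 6.2.2, SAP 7.2.2).
- It stops the infusion (Protocol 9.4 F).
- It appears to count toward the DSMB safety evaluation triggered by three subjects (Protocol 5 and 12.5, where the term is pre-specified clinically important events).

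The rules that admit a patient to infusion do not limit FiO2. Stable baseline in Protocol 9.4 A is "Transcutaneous oxygen saturation in the target range of 88-95% without any increase in ventilator settings", together with stable vasopressor use. Protocol 9.4 D withholds product if the PaO2/FiO2 "ratio is equal or greater than 250 mmHg on this pre-infusion arterial blood gas", which excludes only better oxygenation. Protocol 9.4 B(a) defines one form of clinical instability with the same two-part FiO2 and PEEP condition.

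**The concern.** The item measures a change in ventilator support, and support has a physical maximum. A patient already close to that maximum can deteriorate without being able to show the required change. The vasopressor item beside it can be met in several ways, including the addition of a third agent; the hypoxemia item has one route, and both parts of it must be satisfied.

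The patients affected have little oxygenation reserve, so a fall after infusion matters most in them. They stay in the safety denominator but cannot add to the numerator of this item. At stake are the sensitivity of the between-arm comparison for a harm the protocol singles out, and of a DSMB trigger that works on an absolute count.

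**Working it through.** The plan gives no figure for this point, so there is none to reproduce. The check is whether the definition can be met.

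**1. FiO2 condition.** Inputs: required rise 0.2 (Protocol 6.2.2, 12.1; SAP 7.2.2); maximum FiO2 1.0, the fraction for pure oxygen and the top entry in both Appendix D tables.

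Headroom = 1.0 - pre-infusion FiO2, and the item needs headroom of at least 0.2. Hence pre-infusion FiO2 must be at most 0.80.

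| Pre-infusion FiO2 | Headroom | Attainable |
|---|---|---|
| 0.70 | 0.30 | yes |
| 0.80 | 0.20 | yes, just |
| 0.85 | 0.15 | no |
| 0.90 | 0.10 | no |
| 1.0 | 0 | no |

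Both conditions must hold, so failing this one closes the item.

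**2. Can such a patient be infused?** Yes. Entry and the pre-infusion blood gas set only an upper PaO2/FiO2 limit of 250, and the stability rule limits changes in settings, not their level. At the Appendix D target PaO2 of 55-80 mmHg, FiO2 above 0.8 implies PaO2/FiO2 below 80/0.8 = 100. These patients therefore fall within the below-150 randomization stratum. The converse fails: PaO2 70 on FiO2 0.5 gives 140, which is in the stratum but well under the ceiling.

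**3. Appendix D settings.** On the lower-PEEP table, 4 of 14 columns have FiO2 above 0.80 (0.90 three times, 1.0 once). On the higher-PEEP table, 3 of 14 do (0.90 once, 1.0 twice). Columns are not patients, so this shows only that such settings are anticipated.

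**4. Consequence for counts.** Let s be the share of each arm starting above 0.80 and p the true risk of the harm, taken as equal above and below the ceiling. The countable rate is p(1 - s), and the risk difference becomes (1 - s)(p1 - p0). The risk ratio is unchanged. The documents give neither s nor p; the values below are assumptions.

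| s | Events among 60 at p = 5% | Events among 60 at p = 10% |
|---|---|---|
| 0 | 3.0 | 6.0 |
| 5% | 2.85 | 5.7 |
| 10% | 2.7 | 5.4 |
| 20% | 2.4 | 4.8 |
| 30% | 2.1 | 4.2 |

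Sixty is the size of one arm and also of the interim safety review. If the risk is higher above the ceiling than below it, the proportion of events lost exceeds s.

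**The case against.** The strongest reply is that other routes remain, and much of it stands.

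- **Other events.** A patient above the ceiling can still register the vasopressor, arrhythmia, transfusion-type and 24-hour arrest or death items. Hypoxemia judged to be associated with the product, or unexpectedly severe, is reportable (Protocol 6.2.2, 12.1, 12.2). The isolated transient episode given as not reportable is one related to positioning or suctioning. An unexpected serious adverse event also counts toward the three-subject trigger. A reader might infer that the sickest patients are shut out of the safety endpoint altogether; the documents do not support that. What they lose is the objective criterion that needs no attribution.
- **Bedside protection.** The investigator may stop the infusion for any concern (Protocol 9.4 F), so stopping does not depend on this item alone.
- **Other measurement.** Arterial gases are taken at the end of infusion and at 6 hours, and the oxygenation index rises as PaO2 falls even at FiO2 1.0. That is true, but the index is the efficacy endpoint and produces no reported safety event.
- **Balance.** A reader might infer bias in favour of hMSCs. Randomization is stratified at PaO2/FiO2 150, so the gap should fall on both arms about equally. The effect is lost sensitivity and a smaller absolute difference, not distortion from unequal arms.
- **A second ceiling on PEEP.** A reader might also infer that a patient at PEEP 20 or more cannot gain 5, because both tables stop at 24. Appendix D says "There are no requirements for maintaining a specific PEEP to" FiO2 ratio, so 24 is not a protocol limit. Two more columns of the higher-PEEP table would fail on that reading, but only against a non-binding table.
- **Evidence of high settings.** Appendix G withholds mini-BAL at FiO2 "greater than 0.70 AND PEEP greater than 14" cm H2O. That is a day-2 contraindication and says nothing about settings before infusion.

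**Conclusion.** The point holds for the hypoxemia item. Above a pre-infusion FiO2 of 0.80 the item is unattainable by arithmetic; at exactly 0.80 it can just be met. The same wording stands in three places, and nothing in the entry or stability rules keeps such patients from being infused. Following the plan as written under-counts this harm in both arms, shrinks the absolute risk difference, and makes the three-subject trigger less sensitive, assuming the trigger's term covers these events.

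The size is unknown. A reader might put a patient count on it from the Appendix D columns or the below-150 stratum, but neither gives the distribution of pre-infusion FiO2. The 5% to 30% range rests on assumption, and the proportional loss also assumes equal risk above and below the ceiling.

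**What to change.** In SAP 7.2.2 and 12.7.11:

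1. Report by arm the number of patients whose pre-infusion FiO2 is above 0.80, stating which pre-infusion reading is used.
2. Present the incidence of the hypoxemia item in all treated patients and again in those able to meet it. The split uses a pre-infusion value, so treatment cannot affect it.
3. For reporting and analysis only, add a supplementary summary of post-infusion oxygenation worsening in patients above the ceiling, drawn from the FiO2, PEEP, SpO2 and blood-gas data already collected. The sponsor should define it before unblinding and derive it blinded.

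Separately, the sponsor must reconcile the two-part definition (Protocol 6.2.2 and 12.1, SAP 7.2.2), the same wording in Protocol 9.4 B(a), and the infusion-stopping passage in 9.4 F with the absence of any FiO2 limit at infusion. No clinical threshold is proposed here.

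The cost is a little more analysis and no new data collection. One limitation remains: under Protocol 10.3, settings are recorded every 15 minutes during infusion but only hourly for the next 5 hours, so the duration of a post-infusion episode will be coarse.
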